### **1.1.6 Weight gain**

An interventional study was done by Norimah et al. (2018) on infant weight gain patterns at Pusat Perubatan University Kebangsaan Malaysia (PPUKM) between an experimental group of infants mean score gestational age  $M=38.13$ ;( $SD=2.05$ ) and a control group mean score

gestational age M=37.6 (SD= 2.26). The findings revealed that, within four weeks, the weight gain pattern for the intervention group of infants had increased significantly ( $p<0.00$ ). In the experimental group, the weight gain had increased from 2.89 kg to 3.38kg compared to the control group, which gained from 2.98kg to 3.33kg after the four week study period. However, the study only explored the efficacy of breastfeeding and weight gain patterns among term babies. No study has been done in a local setting regarding the efficacy of KC in association with weight gain among premature infants. Therefore, the researchers would like to explore the weight gain status of preterm infants in relation to KC and breastfeeding rates.

### **1.1.7 Breastfeeding rates**

During the last trimester, preterm infants are unable to get adequate nutrients and immune response components passed from the placenta because their organs and systems are not fully mature. This is why they need special attention and also more breast milk (Arslan & Yeniterzi, 2013; Bağ, Yaprak, Halıcıoğlu, Parlak, & Harputluoğlu, 2006). Therefore, breastfeeding should be regarded as a priority for its nutritional, immunological, psychological and economic benefits. The NICU is a medically complex setting and mothers require adequate guidance to cope with the various changes in their roles. The environment is a good indicator of whether breastfeeding learning will fail or succeed (Norimah et.al.,2018). Mothers depend on nurses to provide reliable, informative and exact breastfeeding knowledge regarding their high-risk infant's care. Despite the mother having obtained a background knowledge of such information via websites, reliable information on breastfeeding should be provided by health care professionals (Norimah et al., 2018).

Nonetheless, the United Nations International Children's Emergency Fund (UNICEF,2018) estimates that 77 million babies worldwide do not get breast milk in their first hour of life, which can increase the risk of neonatal mortality by up to 80%.

Therefore, breastfeeding or expressed breast milk (EBM) is the essential nutrient that enhances the growth and development rate of premature infants (Brown, Raynor & Lee, 2011).

The Second National Health and Morbidity Survey (NHMS II) found that in Malaysia there was an 88.6% overall prevalence of children breastfed for some period of time. At 4 months postpartum, the prevalence of exclusive breastfeeding was just 29% (Fatimah et al., 1999). The Baby-Friendly Hospital Initiative (BFHI) was introduced in all government hospitals in 1983. A subsequent national survey conducted in 2006 found that the overall prevalence of exclusive breastfeeding in Malaysia for babies under 4 months of age fell to 19.3%, 15.5% and 23.9%, while the overall prevalence of exclusive breastfeeding below 6 months was dropped to 14.5%, 11.7% and 17.9% (Fatimah et al., 2010).

The survey also revealed that exclusive breastfeeding was substantially more common in rural areas (30.7%, 95 % CI 23.3-39.2) compared to urban areas (12.9%, 95 % CI 8.9-18.5) Fatimah et al. Al., (1990). The available data at the Kuala Lumpur Maternity Hospital (MHKL) showed that up to 100 % of mother-infant dyads were breastfeeding and 92.2 % were breastfeeding exclusively prior to hospital discharge (MHKL Department of Obstetrics and Gynaecology, 2010). While almost all Malaysian mothers start breastfeeding, Malaysia has the lowest prevalence among Southeast Asian countries of 6-month exclusive breastfeeding rates (Fatimah et. al., 2010). Literature has been developed on the consequences of formula feeding (Sulaiman et. al., 2013). Most infants do not receive the World Health Organization's mandated 6-month exclusive breastfeeding (WHO 2001; Al-Sahab et.al., 2010). Previous research indicated that working women need to be encouraged by their close relatives and their colleagues at work in order to continue breastfeeding after returning to work. It is a public health concern as 70 % of women in urban Malaysia are working and the remainder are working in their reproductive years (Fatimah et al. 2010).

There is no constitutional provision in Malaysia for women workers to breastfeed (or express milk) at work (Hassan, 2014). Previous research in the Kuala Muda District by Azri, Azrina, & Maheran (2017), found that childcare workers may also serve as another potential resource in registered nurseries to maintain exclusive breastfeeding. The encouragement of breastfeeding in part or exclusively for each person involved in taking care of the baby, therefore, has a major role to play in promoting partial or exclusive breastfeeding.

#### **1.1.8 Structured teaching program on kangaroo care.**

At Bogota's second International Workshop on KC, Colombia, it was announced that KC is a fundamental right of the newborn for handling low birth weight in all settings and at all care levels in all countries. Therefore, to support the above fact, KC training must be organized and it requires the efforts of the mothers and nurses for KC implementation in the neonatal environment. Nevertheless, only a few hospitals in Malaysia have initiated KC i.e; Pulau Pinang, Klang Valley, Seremban and Kelantan, but with limited information regarding the guidelines and protocol for KC with preterm infants.

The researchers took this opportunity to comprehensively assess the mothers' and nurses' perspectives towards KC implementation on perception, knowledge, perceived barriers, stress, and practice of KC. Therefore, the aim of this study was to further explore the effectiveness of a KC-EP provided for mothers and nurses regarding preterm infant outcomes at 3 months old on in terms of weight gain, LOS and breastfeeding rates after conducting a KC-EP for mothers and nurses in the NICU, Malaysia.

Several studies suggest that KC is a fundamental component of a developmentally appropriate treatment for hospitalized premature intervention that sustains beneficial effects for infants in the short and long term (Ludington-Hoe, 2013). However, no article has been published to prove the effectiveness of KC, with proper structured teaching, guidelines, and

protocol for KC to be safely implemented among premature infants, in terms of weight gain, LOS, and breastfeeding rates in the Malaysian setting.

## **1.2 Problem Statement**

Prematurity among births and morbidity is increasing and prolongs the separation of infants from their mothers. KC is not yet standardized and is not widely implemented, and our nurses are not committed to KC techniques. Possibly this may be due to lack of commitment, lack of awareness and/or, lack of knowledge among nurses and mothers in the NICU.

There is no formal training on KC techniques. Based on an in-depth analysis of the existing literature, it was decided that a scholarly intervention would be the best information transfer tool for this research, explicitly targeting mothers and nurses to overcome the above issues. The educational intervention designed for this study included theoretical and practical sessions of KC using guidelines, principles and procedures from the United States Institute for Kangaroo Care (USIKC, 2018).

Kangaroo Care is globally recognized as effective interventions and is recommended as routine neonatal care in the NICU. However, this practice is uncommon in Malaysia and only a few hospitals have implemented KC, but without proper guidelines or protocols. From our observations, not every mother recognizes a natural maternal bonding attachment with her preterm infant in the NICU. Therefore, it is important to obtain empirical evidence in order to explore the perception, knowledge, and perceived barriers to KC as well as levels of stress of those whose premature infants are admitted to the NICU. The researchers also evaluate nurses' personal beliefs regarding their perceptions, knowledge and practices in support of KC as a routine nursing intervention in the NICU for the quality of premature infant care.

In addition, the limitations of contextual curriculum resources in nursing subjects may affect the quality of trained nurses and prevent KC from being implemented in the hospital environment. Limitations such as facilities, shortage of staff, availability of experienced staff,

and insufficient number of nurses trained in KC prevented the implementation of KC in hospitals (Lee et al., 2012). Certain current or potential obstacles, according to Ghani, Edvardsson, & Amir (2019), include the lack of comprehensive policies and guidelines to endorse KC procedures, and the lack of ability and incentive to adopt KC techniques. Mothers are not interested in KC, there is a lack of professional cooperation, there are personnel and time constraints, and a medical birth climate that does not prioritize KC involvement, as well as limited resources to enforce KC. Nurses are, therefore, the key drivers in providing relevant information and positive views regarding response to KC, knowledge of KC and ability to implement KC techniques. In a year, more than 15 million babies are born too early. More than 1: 10 infants (Liu et al., 2016) die each year from complications due to a preterm birth. According to the World Health Organization [WHO] (2018), complications of a preterm birth are the prominent cause of death for children under 5 years of age and were responsible for about 1 million deaths in 2015. The inequality in global survival rates is serious. Some premature infants born at 32 weeks of age suffer from a lack of qualified cost-effective treatments, such as supplying comfort for breastfeeding, and critical care for infections and respiratory problems. The use of sub-optimal technology in a low-income setting has led to an inability to care for neonatal preterm infants (WHO, 2018). For example, over 90% of preterm infants (less than 28 weeks) who are born in low-income countries (die?) within the first few days of life, while less than 10% of preterm infants die in high-income countries (WHO, 2018). As reported by the Vital Statistics of Malaysia, (2019) the incidence of live births was 501,946, while the number of deaths was 172,031. The average death rate was 1 death every 3 minutes, 20 deaths per hour and 471 deaths a day. In addition, neonatal mortality <28 days was 46 deaths per 10,000 live births. Of these, the male mortality rate (57.5%) was higher than the female (42.5%). However, for the death of a baby less than 1 year there were 72 deaths for every 10,000 live births. Subsequently, as reported

by the University of Malaysia Medical Center (UMMC), Department of Patient Information Management, Department of Statistics (2017), there were 5,495 total births in 2011 compared to 5,298 in 2015. This indicates a decline in births from 2011 to 2015. However, the number of premature infants increased from (2.54%, n=140) in 2011 to (8.49%, n=450) in 2015 and required special treatment in the NICU. Prematurity of infants with low birth weight (LBW) is a common problem in Malaysia. This is similar to a large population study, carried out in Austria by Waldhoer, Wald, & Heinz (2008), of 10,240 infants. Malaysian mothers' lower weight before pregnancy was a major risk factor associated with LBW infants. To my knowledge, only a few related studies have been conducted in Malaysia. In view of the limited research on KC in premature infants in Malaysia, the objective of our study was to evaluate the effectiveness of KC for premature infants in terms of weight gain and maintaining breastfeeding rate.

Seeing the increasing number of premature infants delivered in Malaysia, the feasibility of gradually implementing KC in Malaysian hospitals is valued. In addition, in this study, the researchers found that not only the mother's personal belief about KC but also nursing expectations were essential in assessing the efficacy of KC for premature infants in this environment. Therefore, exploring KC implementation for both parties who care for the premature infant will help to support and improve the quality of premature infant outcomes.

The incidence of premature infant prolonged hospitalization in neonatal settings appears to be increasing. Although comprehensive studies and clinical initiatives designed towards its reduction have been done abroad, no study has been conducted yet in Malaysia. In relation to this, according to the Little Aussie Premature' Foundation (2017), from 190 premature births, the average length of hospital stay was from 36 to 11 days depending on their gestation, from 32 to 36 weeks of gestation, when born. However, according to Dimes Perinatal Data Center (2011), the average hospital stay for newborns admitted to the NICU was 13.2 days, while

those born at 34 -36 weeks and admitted to a special care center stayed an average of 4.9 days longer than those born at 39-41 weeks. Biswas, Malpani & Ekka (2016) found that the KC group was discharged earlier than the control group with means of (11.4±4.3 vs 17.68±8.64) days ( $p<0.05$ ) among newborns with a birth weight less than 1500gram at a hospital in central India. Jefferies (2011) revealed that KC was reduced in hospitalization for low birth weight infants. The LOS among premature infants was studied in a systematic review and meta-analysis of randomized controlled trials on probiotics preventing candidal colonization and invasive fungal sepsis in preterm neonates by Hua-Jian., Guo-Qiang., Qiao., Christi., & Zhong (2017). This study revealed that candida is the third most common cause of late-onset sepsis in preterm infants in NICUs, and invasive fungal infections have increased dramatically at a range of 1.6% to 9% in VLBW; < 1500 g is associated with an increase in the LOS. Therefore, implementing the KC technique in the NICU setting will help to decrease hospitalization stay and reduce infection among premature infants in Malaysia.

The Newborn Guidelines of the World Health Organization (WHO, 2013) recommends that post-natal mothers continue appropriate, successful, or exclusive breastfeeding for their infants for the first six months. The Baby-Friendly Hospital Initiative (BFHI) promotes breastfeeding in antenatal and postnatal settings around the world and has demonstrated substantial increases in breastfeeding levels and practices everywhere it is implemented (Nyqvist, Haggkvist, Hansen, et al., 2012). Malaysia's government, especially the Ministry of Health, has already done a tremendous job of promoting breastfeeding. However, according to Bachtiar, Hussain, Lanham-New., & Horton (2011) in their study in the Klang Valley, only 33% of mothers were breastfeeding their infants at four months and, by six months, just 21% of mothers had breastfeed their infants exclusively.

At the same time, although Malaysia's government has actively endorsed breastfeeding in all of its hospitals, the pick-up rate for breastfeeding is still unsatisfying. The same resource

shows that most mothers practice KC techniques to breastfeed their premature infant, so KC will help to achieve the goals of the National Breastfeeding Policy (NBP), at least for the first three months after discharge. The findings suggest that during hospitalization mothers really need reliable information and support from nurses. However, the workload of nurses and strict monitoring of premature infants in the NICU will affect the process and delay the delivering of health education on breastfeeding.

Therefore, evaluating the awareness of mothers regarding breastfeeding their preterm infants during hospitalization and mothers' willingness to continue breastfeeding before being discharged is important to enable mothers to continue breastfeeding after returning home. In the recent study done by Norimah, Marlina & Rashidah, (2018) it was stated that the breastfeeding failure rate was due to NICU staffing environment. The main reason was the lack of continuity of nurses to teach and advise mothers individually on breastfeeding at the community and health center level. According to Alina & Zaharah (2010), the mothers reported receiving contradictory guidance on breastfeeding in the NICU, and had various difficulties in initiating breastfeeding, ranging from concerns about the health of their premature infant to lack of knowledge and support in the NICU. Regarding the environmental issues the mothers and premature infants were kept apart due to sickness or employment. Even though they are separated, it is important to enable mothers to care for their premature infants (Norimah et al., 2018). Each mother needs to understand how to express breast milk (EBM) to feed her preterm infant in order to sustain lactation in a separation situation. However, breastfeeding of premature infants in the NICU depends on early and successful support for breast milk expression. The researchers found that the NICU environment and the staff's approach to promoting breastfeeding were a barrier in the context of successful conveyance of knowledge.

Therefore, this study attempts to address the gap by assessing the barriers and enabling breastfeeding through implementing the KC technique with premature infants. In relation to this, the researchers understand that practicing KC will also help to promote NBP goals i.e. an appropriate or exclusive breastfeeding effectuation until at least three months old. Therefore, the need to express breast milk (EBM) or earlier breastfeeding itself is paramount to help little preemies remain appropriate for breastfeeding, gain weight and weigh at least 1.8kg before being discharged. Moreover, it has become a major challenge for nurses, particularly for NICU staff, to encourage maternal participation in the care of their preterm infants in the NICU (Wigert, Hellstrom, & Berg, 2008). Studies have shown that mothers have not been offered the right conditions to participate in caring for their premature infants in the NICU. Having her premature infant admitted to the NICU may negatively affect the mother's ability to care for her premature infant, especially during her infant's hospitalization. Prior to a mother's participation, maternal stress levels in handling her infant's admission (Ahn & Kim, 2007; Brecht et al., 2012; Chourasia, Surianarayanan, Adhisivam, & Bhat, 2013; Howe, Sheu, Wang, & Hsu, 2014), and NICU related maternal ability (Lee, Wang, Lin, & Kao, 2013) need to be evaluated. This is to ensure that a better strategy that would benefit both the mother and their premature infants can be implemented. Hence, it is very important to conduct an intervention study to create a solid basis to guide nursing practice in the NICU; this would have a progressive influence on the preterm infant's growth and development in order to reduce maternal stress (Melnyk & Fineout-Overholt, 2011).

It is also not known whether the didactic intervention would directly influence the perceptions of mothers and nurses; enhance the application of KC; and improve premature infant outcomes. The purposes of the study are described in the following section.

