### **1.1.5 Maternal Stress**

Prematurity is a condition that may hinder or interfere with parenting interactions between the mother and the preterm infant by preventing the mother from holding and caring for her baby (Coşkun & Günay, 2020; Çelebioğlu, & Polat, 2010; Törüner & Büyükgönenç, 2017). According to Brandon et al. (2011), Howland, Pickler, Mccain, Glaser & Lewis (2011), following their premature infant's admission to the NICU, mothers may experience developed background anxiety and stress pertaining to prematurity, lack of familiarity and opportunity in relation to neonatal care, that may change their primary motherhood capability.

In addition, circumstances such as premature infant prognosis, uncertainty, fear of failure, inability to perform maternal roles, and feelings of distress and fatigue may cause mothers to

experience numerous worrying feelings such as anxiety, confusion and stress (Alışır, Şeker, Güler, Anaç & Türkmen, 2010; Erdem & Çelepkolu, 2014). The high levels of stress suffered by premature infant mothers are one of the most significant factors prohibiting mothers from getting involved in breastfeeding and neonatal care (Küçükoğlu, Aytekin, & Gülhaş, 2015). In contrast, other studies reported that mothers have poorer physical health related to the insecurity of their premature infant's health status, which may affect their emotions. The stress and exhaustion felt by mothers may also adversely affect their post-birth stress (Hill & Aldag, 2007; Mortazavi et al., 2014).

Mothers who have LBW infants lack confidence to care for their infants (Smith, Bergelson, Constantian, Valsangkar, and Chan, 2017). It could happen that young mothers do not realize that the nature and effect of their attachment with their premature infant could have a big impact because they have insufficient knowledge, exposure and abilities, and they may not be physically or psychologically mature enough for reproduction (Kuo, Chuang, Lee, Liao, Chang, & Lee, 2012). This research is aimed to evaluate the effect of KC education on perception, knowledge and perceived barriers to KC on preterm infant-mothers' confidence levels and their capability to perform KC. Research conducted by Cho, Kim., Kwon, Cho, Kim, Jun, & Lee, (2016) revealed that KC had a constructive effect on physiological functions such as respiratory rate, enhanced bonding, safely and efficiently reduced stress on mothers, plus contributed to infant's weight gain.

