regarding the initiation of KC with premature infants with monitoring devices, with premature infants with ventilator support, and overcoming perceived barriers, and improving skills and attitude in relation to KC implementation among preterm infants (28 to 36+ 6 weeks' of gestation). The practical session is intended to enable nurses and mothers to gain knowledge and skills related to the KC technique following the guidelines provided for premature infants. How the mothers and nurses perform is documented in the checklist provided at the posttest, but the skills are not evaluated as is beyond the scope of this study. There are, however, factors relating to staff, patients, and doctors that have been highlighted as obstacles to the effective adoption of these techniques and algorithms (Miller et al., 2012; Tanios et al., 2009). Therefore, in this current study, these barriers must be identified to enhance the success of adoption and increase the willingness of mother-infant dyads and nurses to practice KC for premature infant quality of care.

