### 3.16.1 Data Collection Method for Mothers in the Control Group

Based on the day of the preterm infant's admission to the NICU, the researcher screened and recruited its mother into the control group. The mothers and premature infants were medically and surgically stable. The researchers chose mothers who were ready and returned after 48 hours to meet those who were interested to participate in the study. The selection was determined according to the mother's and premature infant's condition (clinically stable and eligible to perform KC), while the length of gestation had to be between 28 to 36/6 weeks. The study samples were selected from early February 2018 to the end of July 2018, within six months of the mothers in the control group. An average of two to four mothers was recruited per week. Mothers had to fill out a consent form. Consent was obtained from all mothers before they were recruited. The researchers contacted the participants in order to give an explanation of what was involved.

Questionnaire I for mothers was provided in an English and bahasa Melayu version. All mothers were given the same questionnaire in three phases ; T0, T1, and T2. At T0, all mothers were given the questionnaire on a voluntary basis to determine their perspectives on the implementation of KC as a baseline. The researchers created an identification code number for each of the mothers to be placed on the envelopes. Thus, mothers' answers could be matched for the T0, T1, and T2 questionnaires. The identification code started from MCG01 (mother control group 01). After a welcome speech and briefing (10 to 15 minutes), the questionnaires were given to the mothers to fill in and then collected. The mothers in the control group were also given a Kangaroo Care Progress Record (KCPR) booklet to record weight gain, feeding status, the routine practice of KC in the clinical setting and after discharge until 3 months old but without any information or input related to KC.

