categorical variables are both independent and dependent variables. Therefore, covariance analysis was used to correct the observed effects on the outcome variables of potential confounders. The summary of the statistical analysis used for all research questions is outlined in Table 3.14. Each of the statistical tests is two-tailed. A p-value below 0.05 was assumed to show statistical significance.

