### 7. Do you have a certificate of neonatology?

01. Yes  02. No

8. How many years you are working in NICU ? \_\_\_\_\_ (*please specify*)

Before you completing the survey, please answer the following question, then go on to the Section B. Do you practice KC in NICU in any way? (Circle your response)

1. NO

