### Part III : Practice on KC

**Instruction:** Please describe how comfortable are you to initiate KC on baby with the following items? Use the following scale:

5 = Very Comfortable

4 = Somewhat Comfortable

3 = Neither Comfortable Nor Uncomfortable

2 = Somewhat Uncomfortable

1 = Very Uncomfortable

No.	Statement	5	4	3	2	1
1	Baby with intravenous catheters.					
2	Baby during the perioperative period.					
3	Baby with endotracheal intubation.					
4	Baby with high-frequency rate or ventilator mode.					
5	Baby with nasal cannula oxygen (nasal prong).					
6	Baby with Nasal Continuous Positive Airway Pressure (NCPAP).					
7	Baby with percutaneous central lines.					
8	Baby with phototherapy treatment.					
9	Baby with Umbilical Arterial Catheters (UAC).					
10	Baby with Umbilical Venous Catheters (UVC).					
11	Baby with anotrope/vasopressors.					

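### Nurses' practice is judged from 11 comfort ratings alone, the graded skill test has no analysis, and KC hours recorded in both groups have no stated role as a between-group outcome

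*Combined protocol and SAP*

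**What the plan says.** **Nurses.** Objective 3 (Section 1.5.2) compares nurses' practice before and after the programme, and H3 (Section 1.6) says that the programme can improve it. Section 1.7.9 defines practice operationally as competence, confidence and responsibility in starting KC. Section 1.2 frames the same outcome as belief: "The researchers also evaluate nurses' personal beliefs regarding their perceptions, knowledge and practices in support of KC as a routine nursing intervention". The instrument is Part III of Questionnaire II (Appendix H), 11 items under one stem: "Please describe how comfortable are you to initiate KC on baby with the following items". Table 3.4 row 5 analyses perception, knowledge and practice as mean scores.

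Two other sources bear on practice. Section A of Appendix H asks "Do you practice KC in NICU in any way? (Circle your response", which Section 3.10.1 lists among the demographic variables. Section 3.17 has all 47 nurses give a return-demonstration, graded pass or fail. On the checklist, Section 2.5.2 says that performance is "documented in the checklist provided at the posttest, but the skills are not evaluated as is beyond the scope of this study".

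**KC actually done.** Section 1.2 says it is not known whether the teaching would "enhance the application of KC; and improve premature infant outcomes". Section 2.6 aims to assess the compliance of mothers and nurses in providing KC. Control mothers receive a booklet to record, among other things, "the routine practice of KC in the clinical setting and after discharge until 3 months old". Section 3.16.4(a) names KC duration first among the infant outcome variables, and Section 3.20.1 sorts it into six weekly classes. Table 3.4 lists KC performance in row 1 and KC compliance in rows 2 and 4.

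**Background aim.** Section 1.1.5 says the research will evaluate "the effect of KC education on perception, knowledge and perceived barriers to KC on preterm infant-mothers' confidence levels and their capability to perform KC". Section 1.1.3 has a similar sentence.

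**The concern.** A nurse can feel more comfortable about KC seven days after training without starting it more often or doing it better. If the Part III mean rises, the plan as worded reports improved nursing practice. The one observed measure of skill would go unreported, and readers would meet contradictory statements on whether skill was assessed at all.

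For the dyads, H2 attributes infant effects to KC itself, while the comparison is between a group offered the programme and a group under routine care. Section 3.16.1 leaves KC open to control mothers who want it. Unless KC hours are compared between groups, a null infant result could mean that KC did not help or that the groups received similar amounts. A positive result could not be tied to KC either, as distinct from other differences between two groups recruited in successive periods.

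**Working it through.** The plan has no figure of its own on this point. Its one sample-size calculation (Section 3.7.2) concerns weight gain: 2 × 2.802² × 0.64 / 0.54² ≈ 34.5, so 35 per group, and 35 / 0.70 = 50. It reproduces, but gives no basis for nurses' practice or KC hours. The check is mainly a comparison of sections.

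**1. Does the practice score measure practice?**
- Section 1.7.9 names three components: competence, confidence, responsibility.
- All 11 items of Part III ask for comfort with a given line, device or condition. Items asking what the nurse does: 0 of 11.
- Comfort reaches at most the confidence component.

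**2. How easily could comfort alone carry H3?** Take 47 nurses with complete pairs, 80% power, a two-sided test and the plan's threshold ("A p-value below 0.05 was assumed to show statistical significance"). The detectable mean change, by normal approximation, is 2.802 / √47 = 0.41 SD of the change. A moderate rise in comfort would be enough.

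**3. Is observed skill analysed?**
- Section 2.5.2: skills not evaluated, out of scope.
- Section 3.15.5: a checklist is prepared to evaluate the skill steps.
- Section 3.17: return-demonstration graded pass or fail.
- Section 3.18: a checklist assesses each nurse's confidence and skills.
- Table 3.4: no row for the result.

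The first statement conflicts with the next three, and the result has no analysis under either reading.

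**4. Is KC duration a between-group outcome?**
- Recorded in both groups: Section 3.9 (Section B), 3.16.1, 3.16.4 and 3.20.1.
- Named in Sections 1.4 to 1.6: only in the preamble to 1.4, as compliance; in no numbered question, objective or hypothesis.
- Table 3.4: listed beside chi-square, general linear model and, in rows 2 and 4, t-test. The questions of those three rows concern mothers' scores, weight gain and breastfeeding. Nothing says whether KC duration is outcome, covariate or descriptive.

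**5. Can a difference in exposure be assumed?** Section 3.16.1 has control mothers visiting once a day for 30 minutes to 1 hour. If every visit were spent in KC, that is 7 × 0.5 = 3.5 to 7 × 1 = 7 hours a week. The experimental target in Section 3.11 is 4 to 5 hours a week. The control figure is a ceiling and true use may be far lower, but the plan gives no ground for taking it as nil.

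**6. Could the comparison be informative?** With 48 per group, 80% power and a two-sided 0.05 level, the detectable difference is 2.802 × √(2/48) = 0.57 SD. The documents give no SD for weekly hours. Assuming 1, 2 or 3 hours gives 0.57, 1.14 or 1.72 hours a week, all well below the 4-to-5-hour target.

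**The case against.** The strongest reply is that the plan is open about what it measures. Section 1.2 speaks of personal beliefs, and Section 3.10.1 says the Part III score indicates confidence and skills, so renaming the scale is largely a matter of labels. That stands in part: a careful reader can find out what was scored. But H3 and objective 3 carry the word practice without that limit, and the definition in Section 1.7.9 is wider than comfort.

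A second reply concerns KC done. A reader might infer that the records of KC are left out of the tests, or that the trial cannot support any claim about behaviour. The documents do not support either. KC duration is a named outcome variable, is classified in advance, and appears in three rows of Table 3.4 beside named tests. Appendix E(a) also asks each mother whether she practises KC in the NICU, outside the 57 scored items. What remains is that its role and its between-group contrast are not stated.

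A reader might also infer that mothers' capability is concluded from belief items. It is not concluded from anything: it appears only in background text and is absent from the objectives, the hypotheses and Table 3.4. Nor does the completed diary page in the Appendix O(a) flipchart show that session times were charted for all 96 dyads. It is a teaching example, and the data sheet in Appendix F(b) is headed for the experimental group only.

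Finally, the alternative measures are imperfect. The yes/no item asks about practising KC in any way, on a unit where KC already took place. Diary hours may be kept less completely by control mothers, who had no coaching or reminders. Both points stand and limit what the fix can claim.

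**Conclusion.** The point holds in a limited form and should be corrected before reporting. It does not undermine the trial as a whole.

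- H3 can support a statement about nurses' self-rated comfort in starting KC. With 0 of 11 items on behaviour, it cannot support one about what nurses do.
- The pass/fail skill result is collected and graded but unanalysed, and Section 2.5.2 conflicts with Sections 3.15.5, 3.17 and 3.18.
- KC duration is recorded and listed, but has no objective, hypothesis or stated role as a between-group outcome. Section 1.2 asks about application of KC, Section 2.6 aims at compliance, and control mothers may do KC, so an infant result cannot at present be linked to a difference in exposure.

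This assumes that the control booklet does capture KC duration, as Sections 3.9 and 3.20.1 say. The detectable differences assume complete data, and for weekly hours also an assumed SD.

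**What to change.** 1. In H3, objective 3 and Table 3.4 row 5, rename the Part III outcome self-rated comfort in initiating KC, and limit the H3 conclusion to that. At the same time reconcile the scoring direction: Section 3.10.1 reads a mean of 2.26 or below as high confidence, although 5 is the most comfortable answer.
2. Report the nurses' pass/fail return-demonstration descriptively, as observed skill at posttest. There is no pretest grade, and training continued until nurses were skilful, so a high pass rate is to be expected. Reconcile Section 2.5.2 with Sections 3.15.5, 3.17 and 3.18. Report the yes/no practice item before and after as supportive description only, if Section A was completed at both tests.
3. In Table 3.4, state in-hospital KC hours per week as a between-group outcome, with the six classes of Section 3.20.1 as a secondary display. The 4-to-5-hour target lies in the same class as 1 hour, so the classes alone would not show whether it was reached. Many control values may be zero, so give medians and a rank-based comparison beside the t-test.
4. Reword the background aim in Sections 1.1.3 and 1.1.5 so that it does not promise an evaluation of mothers' confidence or capability.

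The cost is wording, one descriptive table and one group comparison on data already collected. The downsides are that H3 claims less, and the yes/no item is broad and may barely change in seven days. KC hours are partly diary-recorded. If control mothers recorded less completely and blanks are read as no KC, the group difference will be overstated; the report should say so and give the completeness of recording by group.
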